**Footnotes:**

- a. Safety visits and early exit visit will be by telephone.
- b. An early exit visit will be conducted as soon as possible for those participants who are unable to continue participation in the study and withdraw from the study before Day 183, but who do not withdraw consent. Participants who wish to withdraw consent from participation in the study will be offered an early exit visit (prior to formal withdrawal of consent).
- c. Signing of the ICF should be done before any study-related activity.
- d. Medical history of all participants will be recorded in the eCRF, including whether each condition places the participant at increased risk for severe RSV disease. The conditions placing a participant at increased risk of severe RSV disease include congestive heart failure, coronary artery disease (such as angina pectoris, ischemic cardiomyopathy, history of myocardial infarct, or history of coronary artery bypass graft or coronary artery stent), and chronic lung disease (such as asthma and chronic obstructive pulmonary disease). As part of the medical history, the investigator must also collect and document risk factors for blood clotting events and thrombocytopenia at screening. As done for any other medical history events, the information must be entered on the relevant eCRF pages such as Medical History page or Concomitant Medication page.
- e. Prestudy therapies administered up to 30 days pre-vaccination must be recorded on Day 1.
- f. Sitting systolic and diastolic blood pressure, heart rate, and respiratory rate after at least 5 minutes rest on Day 1. At non-vaccination visits, vital signs will be measured if deemed necessary by the investigator.
- g. Investigator must check for clinically significant acute illness at the time of vaccination or body temperature  $\geq 38.0^{\circ}\text{C}$  ( $\geq 100.4^{\circ}\text{F}$ ) within 24 hours prior to the planned time of vaccination. In such cases, the participant may be vaccinated up to, and no later than 10 days after the scheduled vaccination, or be withdrawn at the discretion of the investigator.
- h. After vaccination, participants will remain under observation at the study site for at least 15 minutes for presence of any acute reactions and solicited events. Any unsolicited AEs, solicited local (injection site) or systemic AEs, and vital signs (systolic and diastolic blood pressure [sitting], heart rate, respiratory rate, and body temperature) will be documented by study-site personnel following this observation period.
- i. AESIs, including potential AESIs, are to be reported from the moment of vaccination until 6 months after the vaccination. See Section [8.3.6](#).
- j. Concomitant therapies will be collected from the time of study vaccination through 28 days post-vaccination when associated with an AE, and from ICF signature until 6 months post-vaccination when associated with an SAE or AESI.
- k. Any history of SARS-CoV-2 vaccination (name/manufacturer of the vaccine and date of administration, whenever possible) prior to and during the study will be collected in the eCRF.
- l. Rulers and thermometers will be distributed at Visit 1.
- m. Participants will be contacted by telephone 2 to 4 days post-vaccination to remind them to fill in the participant diaries and to check that they are entering information correctly.
- n. Screening and vaccination may be split into 2 visits in consultation with the sponsor or its delegate. Every effort should be made for split visits to occur preferably within 3 to 5 days and no later than 10 days, and pre-vaccination vital signs should be repeated on the day of vaccination if this visit is split.
- o. Aliquots of serum samples collected for immunogenicity tests can be reconverted for participant's safety purposes upon sponsor request. Please refer to [Table 4](#) for a non-exhaustive list of tests that may be requested to be performed on these samples in case of potential AESI reporting.
- p. Includes the assessment of the severity of solicited AEs during the Visit 2 phone call.
- q. Includes the assessment of the severity of unsolicited AEs and the occurrence of special reporting situations during all visits up to 28 days post-vaccination, including the Visit 2 and Visit 4 phone calls.

## 2. INTRODUCTION

The respiratory syncytial virus (RSV) vaccine that will be investigated in the current study, the Ad26/protein preF RSV vaccine (VAC18193), is a combination of 2 vaccine components, administered as a single intramuscular (IM) injection:

- Ad26.RSV.preF (JNJ-64400141), a replication-incompetent adenovirus serotype 26 (Ad26) containing a DNA transgene that encodes the prefusion conformation-stabilized F protein (pre-F) derived from the RSV A2 strain.
- RSV preF protein (JNJ-64213175), a recombinant pre-F protein derived from the RSV A2 strain.

For the most comprehensive nonclinical and clinical information regarding the Ad26/protein preF RSV vaccine, refer to the latest version of the Investigator's Brochure (IB) for Ad26/protein preF RSV vaccine ([IB Ad26/protein preF RSV vaccine 2021](#)).

The term “study vaccine” used throughout the protocol, refers to the Ad26/protein preF RSV vaccine as defined in Section [6.1](#).

The term “sponsor” used throughout this document refers to the entities listed in the Contact Information page(s), which will be provided as a separate document.

### 2.1. Study Rationale

The aim of this study is to demonstrate the non-inferiority of Phase 3 clinical trial material (CTM) compared with Phase 2b CTM\*, as used in the proof of concept study (VAC18193RSV2001) in which efficacy of the Ad26/protein preF RSV vaccine was demonstrated, in terms of geometric mean titers (GMTs) to RSV preF protein using enzyme-linked immunosorbent assay (ELISA) at 14 days post-vaccination (Day 15).

\*Note: in this protocol, “Phase 3 CTM” refers to Phase 3 CTM representative of the commercial material, and “Phase 2b CTM” refers to CTM representative of the Phase 2b (VAC18193RSV2001) CTM.

### 2.2. Background

RSV is an important cause of serious respiratory infections in adults aged 60 years and older, immunocompromised individuals, and those with underlying chronic cardiopulmonary conditions ([Falsey 2005](#)). Exact numbers on the burden of RSV disease in adults aged 60 years and older are limited. In long-term care facilities, RSV is estimated to infect 5% to 10% of the residents per year with significant rates of pneumonia (10%-20%) and death (2%-5%) as a consequence ([Falsey 2000](#)). In the United States, approximately 177,000 hospital admissions and approximately 10,000 to 14,000 deaths per year are due to severe RSV infections in adults aged 65 years and older ([Falsey 2005](#)). These data support the importance of developing a safe and effective vaccine for certain adult populations, such as older adults. Currently, there are no vaccines or specific treatments available for RSV.

Several studies have indicated that high serum neutralizing antibody levels are associated with reduced risk of severe RSV infection in older adults (Falsey 1998; Walsh 2004). There is some indication that decreased protection against RSV in older adults could be attributed to an age-related decline in RSV-specific T-cell function (de Bree 2005; Looney 2002). The Ad26.RSV.preF vaccine component evaluated in this study is based on the AdVac® platform, which has been shown to promote strong humoral and cellular responses (Barouch 2013; Barouch 2018; Data on file; Milligan 2016).

## Nonclinical Studies

For the most comprehensive nonclinical information regarding the Ad26/protein preF RSV vaccine, refer to the latest version of the IB for Ad26/protein preF RSV vaccine ([IB Ad26/protein preF RSV vaccine 2021](#)).

## Clinical Studies

For the most comprehensive clinical information regarding the Ad26/protein preF RSV vaccine, refer to the latest version of the IB for Ad26/protein preF RSV vaccine ([IB Ad26/protein preF RSV vaccine 2021](#)).

## Clinical Safety Experience With Ad26-based Vaccines

Safety data of Ad26-vectored vaccines from the adenoviral vaccine safety database ([AdVac Safety Database 2021](#)), including vaccines against Ebola virus (Ad26.ZEBOV), HIV (Ad26.ENVA.01, Ad26.Mos.HIV, and Ad26.Mos4.HIV), malaria (Ad26.CS.01), RSV (Ad26.RSV.FA2 and Ad26.RSV.preF), filovirus (Ad26.Filo), Zikavirus (Ad26.ZIKV.001), and HPV (Ad26.HPV16 and Ad26.HPV18) have been evaluated in adults.

All the above Ad26-based vaccines were found to be well tolerated in adults, without significant safety issues identified. Several other studies are currently ongoing and no safety concerns have been raised to date.

## Thrombosis With Thrombocytopenia Syndrome

Thrombosis in combination with thrombocytopenia (thrombosis with thrombocytopenia syndrome [TTS]), in some cases accompanied by internal bleeding, has been observed very rarely following vaccination with the Janssen COVID-19 (Ad26.COVID-19) vaccine. Reports include severe cases of venous thrombosis at unusual sites such as cerebral venous sinus thrombosis (CVST), splanchnic vein thrombosis and arterial thrombosis, in combination with thrombocytopenia. The associated symptoms began approximately 1 to 2 weeks after vaccination, mostly in women under 60 years of age. Thrombosis in combination with thrombocytopenia can be fatal. The exact pathophysiology of TTS is unclear. This event has not been observed to date with any other Janssen Ad26-based vaccines. Participants should be instructed to seek immediate medical attention if they develop symptoms such as shortness of breath, chest pain, leg swelling, persistent abdominal pain, severe or persistent headaches, blurred vision, skin bruising or petechiae beyond the site of vaccination.

## 2.3. Benefit-Risk Assessment

More detailed information about the known and expected benefits and risks of the Ad26/protein preF RSV vaccine may be found in the IB for Ad26/protein preF RSV vaccine ([IB Ad26/protein preF RSV vaccine 2021](#)).

### 2.3.1. Risks Related to Study Participation

The following potential risks for the Ad26/protein preF RSV vaccine will be monitored during the study:

#### Risks Related to Ad26/protein preF RSV Vaccine

The Ad26/protein preF RSV vaccine is being studied in 4 ongoing studies in more than 6500 participants aged 60 years and above, including participants with comorbidities, to assess safety and immunogenicity, and to investigate whether the vaccine prevents RSV disease. In these studies, the most commonly reported solicited local AEs were injection site pain/tenderness and swelling (mild to moderate). The most frequently reported solicited systemic AEs were fatigue, muscle pain, headache, chills, joint pain, and nausea, which were mild to moderate in severity. These solicited AEs were short-lived and resolved within a few days. Overall, available results from these studies show the vaccine to be well-tolerated with no safety concerns.

#### General Risks Related to Vaccination

In general, IM injection may cause local itching, warmth, pain, tenderness, erythema/redness, induration, swelling, arm discomfort, or bruising of the skin. Participants may exhibit general signs and symptoms associated with IM injection of a vaccine and/or placebo, including fever, chills, rash, myalgia, nausea/vomiting, headache, dizziness, arthralgia, general itching, and fatigue. These side effects will be monitored, but are generally short-term and do not require treatment.

Syncope can occur in association with administration of injectable vaccines. Syncope can be accompanied by falls. Procedures should be in place to avoid falling injury. If syncope develops, participants should be observed until the symptoms resolve. Fear of injection might lead to fainting and fast breathing.

Participants may have an allergic reaction to the vaccination. An allergic reaction may cause a rash, urticaria, or even anaphylaxis. Severe reactions are rare. Participants with a known or suspected allergy, or history of anaphylaxis or other serious adverse reactions to vaccines or their excipients (including specifically the excipients of the study vaccine) will be excluded from the study.

After vaccination, participants will remain at the study site for at least 15 minutes and will be closely observed by study staff. Necessary emergency equipment and medications must be available in the clinic to treat severe allergic reactions.

#### Pregnancy and Birth Control

The effect of the Ad26/protein preF RSV vaccine on a fetus or nursing baby is unknown. Participants may therefore only participate if they are postmenopausal (defined as no menses for

12 months without an alternative medical cause) and not intending to conceive by any methods. Participants who are surgically sterile are also eligible for the study. Follow-up information regarding the outcome of the pregnancy will be required.

Because the effect on sperm is unknown, participants must inform the study-site personnel if their partner becomes pregnant during the study. Follow-up information regarding the outcome of the pregnancy will be requested upon the consent provided by the partner.

### **Participants with Immunosuppression/Reduced Immune Response**

Participants with abnormal function of the immune system will be excluded from the study. Limited evidence indicates that inactivated vaccines (or nonreplicating viral vaccines) generally have the same safety profile in immunocompromised patients as in immunocompetent individuals. However, the magnitude, breadth, and persistence of the immune response to vaccination may be reduced or absent in immunocompromised persons.

### **Risks from Blood Draws**

Blood draws may cause pain, tenderness, bruising, bleeding, dizziness, vasovagal response, syncope, and rarely, infection at the site where the blood is taken. Participants with contraindications to IM injections and blood draws (eg, bleeding disorders) will be excluded.

### **Concomitant Vaccination**

Concomitant vaccination might have an influence on both the safety profile and immunogenicity of the Ad26/protein preF RSV vaccine. Likewise, the Ad26/protein preF RSV vaccine might have an influence on both the safety profile and immunogenicity of any concomitant vaccination. As a result, licensed live attenuated vaccines should be given at least 28 days before or after vaccination. Other licensed (not live) vaccines (eg, influenza, tetanus, hepatitis A, hepatitis B, rabies) should be given at least 14 days before or after vaccination to avoid potential confusion of adverse reactions and potential immune interference. If a vaccine is indicated in a postexposure setting (eg, rabies or tetanus), it must take priority over the study vaccine.

For SARS-CoV-2 vaccines either licensed or available under Emergency Use Authorization: live attenuated vaccines should be given at least 28 days before or after vaccination; non-live vaccines should be given at least 14 days before or after vaccination.

A viral-vector SARS-CoV-2 vaccine is not to be given at any time prior to randomization or during the study period until 28 days after study vaccination.

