### Amendment 2 (26 November 2021)

**Overall Rationale for the Amendment:** In view of the slow rate of enrollment in the current study, the following changes were made to the inclusion and exclusion criteria to facilitate enrollment: the upper age limit for inclusion was adapted from less than 65 years to 75 years inclusive; a prior vaccination with a viral-vectored SARS-CoV-2 vaccine is allowed if administered at least 6 months prior to randomization; and it was clarified that co-participation in the observational phase of interventional studies can be allowed upon sponsor approval.

Emerging data from other ongoing clinical studies with the Ad26/protein preF RSV vaccine in participants in the age range of 60 to 75 years show that there is no substantial impact of age on vaccine-induced humoral immune responses, primary analysis pre-F ELISA antibody titers, and vaccine safety between older adults of 60 to 75 years of age. Based on these data, the sponsor considers an upper age limit of 75 years (inclusive) acceptable for this study.

Clinical studies with Janssen's Ad26-vectored SARS-CoV-2 vaccine have not shown a clear impact of baseline pre-existing Ad26 neutralizing antibodies on vaccine-induced responses. Based on these data, the sponsor considers a prior vaccination with a viral-vectored SARS-CoV-2 vaccine acceptable if administered at least 6 months prior to randomization. A minimal window of 6 months has been chosen since humoral immune response data evaluating a potential interference of the anti-vector responses with the vaccine-induced responses in consecutive dosing with viral-vectored vaccines with different inserts are not available to date. During further development of viral-vectored vaccines, data on potential interference will become available; at that point, the time window may be adjusted for future immunogenicity trials. The standard dosing window for viral-vectored SARS-CoV-2 vaccines in other Ad26.RSV.preF-based vaccine efficacy studies is 28 days and does not foresee an impact on safety.

Participants who participate in the observational phase of an interventional study at screening may also be eligible for the current study since participation in the observational phase without product administration will not adversely impact safety of the participants or have an impact on the vaccine-induced immune response.

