Furthermore, additional language referring to laboratory diagnostic tests for the follow-up and assessment of potential adverse events of special interest (AESIs) was added. Clarifications were made with regards to some exclusion criteria, the recording of medical history, and the solicited and unsolicited AE assessments to be performed during phone call visits. It was clarified that screening and vaccination may be split into 2 visits in consultation with the sponsor or its delegate.

Additionally, a few minor updates were made in alignment with the latest Janssen protocol template.

The changes made to the clinical protocol VAC18193RSV3004 as part of Protocol Amendment 2 are listed below, including the rationale of each change and a list of all applicable sections. Changes made in previous protocol amendments are listed in Section 10.7 Appendix 7: Protocol Amendment History.

Section Number and Name	Description of Change	Brief Rationale
Title page 1.1 Synopsis 4.1 Overall Design 5.1 Inclusion Criteria	Inclusion Criterion 3 was amended to expand the eligible age range from 60 to less than 65 years, to 60 to 75 years inclusive.	To facilitate enrollment
5.2 Exclusion Criteria	Exclusion Criterion 10 was amended to allow the use of viral-vectored SARS-CoV-2 vaccines if administered at least 6 months prior to randomization.	To facilitate enrollment
5.2 Exclusion Criteria	Footnote for Exclusion Criterion 13 was updated to allow participants who participate in the observational phase of interventional studies to be enrolled in the study, if approved by the sponsor or its delegate.	To facilitate enrollment
5.2 Exclusion Criteria	A textual change was made to Exclusion Criterion 1 to clarify that participants with a history of malignancy within 5 years before screening, which is considered to have minimal risk of recurrence per investigator's judgement, can be enrolled.	Clarification
5.2 Exclusion Criteria	Exclusion Criterion 7 was amended to restrict the exclusion of participants on treatment with immunoglobulins to those immunoglobulins expected to impact the vaccine-induced immune response.	Clarification
1.2 Schema 1.3 Schedule of Activities 5 STUDY POPULATION 5.5 Criteria for Temporarily Delaying Study Vaccine Administration	It was clarified that screening and vaccination may be split into 2 visits in consultation with the sponsor or its delegate.	To allow more flexibility in timing of screening and vaccination in the best interest of participants.

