### **2.3.3.      Benefit-Risk Assessment of Study Participation**

Based on the available data and proposed safety measures, the overall benefit-risk assessment for this clinical study is considered acceptable for the following reasons:

- The dose levels for Ad26.RSV.preF and RSV preF protein used in the current study were determined from the primary analysis of Cohort 2 in study VAC18193RSV1004 and are currently under further evaluation in studies VAC18193RSV1004 and VAC18193RSV2001. Available safety data from all studies show the vaccine to be well-tolerated with no safety concerns. Based on these data, the dose levels of Ad26.RSV.preF and RSV preF protein selected for the present study are  $1 \times 10^{11}$  vp and 150  $\mu$ g, respectively (Section 4.3). In the primary analysis of study VAC18193RSV2001, vaccine efficacy was demonstrated for these dose levels in adults aged 65 years and above, for the prevention of LRTD caused by RSV.
- Only participants who meet all inclusion criteria and none of the exclusion criteria (specified in Section 5) will be allowed to participate in this study. The selection criteria include adequate provisions to minimize the risk and protect the well-being of participants in the study.
- Safety will be closely monitored throughout the study:

In general, safety evaluations will be performed at scheduled visits during the study, as indicated in the [Schedule of Activities](#).

After vaccination, participants will remain at the study site for at least 15 minutes and will be closely observed by study staff. Necessary emergency equipment and medications must be available in the clinic to treat severe allergic reactions. Participants will use a participant diary to document solicited signs and symptoms. Details are provided in Section 8.2.

The investigator or the designee will document unsolicited AEs as indicated in Sections 8.2 and 8.3 and Section 10.2.

Any clinically significant abnormalities will be followed by the investigator until resolution or until clinically stable.

After vaccination, participants will enter a 6-month safety follow up period for collection of serious adverse events (SAEs) and adverse events of special interest (AESIs).

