  - 7.1 received hematopoietic stem cell transplant in medical history, treatment with immunoglobulins expected to impact the vaccine-induced immune response (including monoclonal antibodies for chronic underlying conditions) in the 2 months, immunoglobulins specific to RSV, human metapneumovirus, or parainfluenza viruses in the 12 months, apheresis therapies in the 4 months, or blood products in the 4 months before the planned administration of study vaccine or has any plans to receive such treatment during the study.

*Note: The investigator is encouraged to contact the sponsor to discuss eligibility of participants on immunoglobulin treatment.*

8. history of TTS or heparin-induced thrombocytopenia and thrombosis (HITT).
9. received or plans to receive:
  - a. Licensed live attenuated vaccines within 28 days before or after planned administration of the study vaccine.
  - b. Other licensed (not live) vaccines within 14 days before or after planned administration of the study vaccine.
10. Criterion modified per Amendment 2
  - 10.1 received or plans to receive a SARS-CoV-2 vaccine:
    - a. Live attenuated SARS-CoV-2 vaccine within 28 days before or after planned administration of study vaccine.
    - b. Non-live SARS-CoV-2 vaccine within 14 days before or after planned administration of study vaccine.
    - c. A viral-vectored SARS-CoV-2 vaccine within 6 months prior to randomization or during the study period until 28 days after study vaccination.
11. received an RSV vaccine in a previous RSV vaccine study.
12. received or plans to receive an Ad26-vectored vaccine at any time prior to randomization until 28 days after study vaccination (for exclusion criteria related to SARS-CoV-2 vaccines, please refer to Exclusion Criterion 10).
13. Criterion modified per Amendment 2
  - 13.1 received an investigational drug or used an invasive investigational medical device within 30 days or received an investigational vaccine within 6 months before the planned administration of the study vaccine or is currently enrolled or plans to participate in another investigational study during this study.

*Note: Participation in an observational clinical study (ie, without intervention) or in the observational phase of interventional studies is allowed upon approval of the sponsor or its delegate.*

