#### **6.8. Concomitant Therapy**

Pre-study therapies administered within the 30 days before administration of study vaccine must be recorded on Day 1. Additionally, any history of SARS-CoV-2 vaccination (name/manufacturer of the vaccine and date of administration, whenever possible) prior to and during the study will be collected in the eCRF.

Concomitant therapies associated with solicited AEs will be collected by the participants in the participant diary from the time of study vaccination through 7 days after vaccination. Concomitant therapies associated with unsolicited AEs will be collected and recorded in the eCRF from the time of study vaccination through 28 days after vaccination. Concomitant therapies associated with SAEs or AESIs will be collected and recorded in the eCRF from ICF signature until 6 months after vaccination.

Analgesic/antipyretic medications and non-steroidal anti-inflammatory drugs may be used post-vaccination only in cases of medical need (eg, fever or pain) and their use must be documented. Use of these medications as routine prophylaxis prior to study vaccination is discouraged.

Information on concomitant use of herbal supplements or vitamins will not be collected.

Use of any experimental medication (including experimental vaccines other than the study vaccine) during the study is not allowed.

Vaccination with licensed live attenuated vaccines within 28 days of a study vaccination (ie, before or after) is prohibited. Other licensed (not live) vaccines (eg, influenza, tetanus, hepatitis A, hepatitis B, rabies) should be given at least 14 days before (or at least 14 days after) administration of study vaccine in order to avoid potential confusion of adverse reactions and potential immune interference. If a vaccine is indicated in a post-exposure setting (eg, rabies or tetanus), it must take priority over the study vaccine.

For SARS-CoV-2 vaccines either licensed or available under Emergency Use Authorization: live attenuated vaccines should be given at least 28 days before or after vaccination; non-live vaccines should be given at least 14 days before or after vaccination.

A viral-vector SARS-CoV-2 vaccine is not to be given within 6 months prior to randomization or during the study period until 28 days after the last study vaccination.

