**Table 2: Analysis Sets**

Analysis Set	Description
All Screened	
This analysis set includes all participants screened for the study, regardless if they were screen failures or they got enrolled in the study.
 
Rescreened participants are counted only once.

Full Analysis Set (FAS)	
The full analysis set (FAS) will include all participants who received study vaccination, regardless of the occurrence of protocol deviations and vaccine type (study vaccine or placebo).
 
All safety and participant information analyses will be based on the FAS.

Per Protocol Immunogenicity Analysis Set (PPI)	
The Per Protocol Immunogenicity Analysis Set will include all randomized participants who received study vaccine and for whom immunogenicity data are available. Samples taken after a participant experienced a major protocol deviation expected to impact the immunogenicity outcomes will be excluded from the PPI analysis.
 
The list of major protocol deviations that would lead to elimination from the immunogenicity analysis is specified in the major protocol violation criteria document, which will be finalized before database lock and unblinding.
 
The primary analysis set for analyses related to RSV immunogenicity is the PPI Set. As a sensitivity analysis, key tables may also be based on the FAS.

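### Does the stricter look-back for viral-vector SARS-CoV-2 vaccines in Protocol Section 2.3.1 call for a change to the plan?

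*Protocol*

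**What the plan says.** Three places in the current protocol give a look-back for a viral-vector SARS-CoV-2 vaccine.

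- Section 2.3.1, under Concomitant Vaccination: "A viral-vector SARS-CoV-2 vaccine is not to be given at any time prior to randomization".
- Section 5.2, Exclusion Criterion 10.1c: "A viral-vectored SARS-CoV-2 vaccine within 6 months prior to randomization or during the study period until 28 days after study vaccination".
- Section 6.8: "A viral-vector SARS-CoV-2 vaccine is not to be given within 6 months prior to randomization".

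On who may enter, Section 2.3.3 says "Only participants who meet all inclusion criteria and none of the exclusion criteria", as set out in Section 5, will be allowed to take part. On the analysis side, SAP Table 2 says that the list of deviations leading to removal from the immunogenicity analysis "is specified in the major protocol violation criteria document, which will be finalized before database lock and unblinding".

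**The concern.** A protocol should carry one rule on prior vaccination. Here the benefit-risk text, which ethics committees and sites read, describes a narrower population than the criteria admit.

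The subject also matters to the endpoint. The study vaccine contains an Ad26 vector, and the Amendment 2 rationale concedes that data on interference "in consecutive dosing with viral-vectored vaccines with different inserts are not available to date".

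If a site applied the stricter sentence, it would turn away people whom the criteria allow, in a study already amended because enrolment was slow. If the deviation list followed the stricter sentence, vaccinated participants could lose samples from the Per-protocol Immunogenicity (PPI) Set, on which the primary comparison rests.

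**Working it through.** **1. The three rules side by side.**

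| Place in the protocol | Look-back before randomization | Bar ends |
|---|---|---|
| Section 2.3.1 | unlimited | 28 days after study vaccination |
| Criterion 10.1c | 6 months | 28 days after study vaccination |
| Section 6.8 | 6 months | 28 days after the last study vaccination |

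The study gives one dose, so the three end points are the same and only the look-back conflicts. Someone vaccinated within 6 months is barred by all three. Someone vaccinated earlier than that is barred by Section 2.3.1 alone. No reading satisfies all three.

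**2. Does another provision settle it?** Exclusion Criterion 12 bars Ad26-vectored vaccines at any time before randomization, but it sends SARS-CoV-2 vaccines back to Criterion 10. It neither explains nor removes the conflict.

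**3. Which text do sites act on?** Section 2.3.3 ties participation to the Section 5 criteria. Section 5 requires questions about the criteria to be settled with the sponsor before enrolment, and allows no waivers. The note closing Section 5.2 tells investigators to confirm the enrolment criteria before vaccinating. Section 5.3 sends the reader to Section 6.8, not to Section 2.3.1, for prohibited and restricted therapy. The two places used in operation agree with each other.

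**4. Does the sample size depend on it?** Inputs from Protocol Section 9.2: SD 1.3 on the log2 scale, margin 2/3, true ratio 1, 2-sided 5% level, 90% power.

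- Margin on the log2 scale: log2(1.5) = 0.585.
- Normal approximation: n = 2 × 1.3² × (1.960 + 1.282)² / 0.585² = 2 × 1.69 × 10.51 / 0.342 = 103.8, so 104 per group.
- Noncentral t: 105 per group, power 0.901.

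The plan's 105 reproduces. None of its inputs refers to vaccination history.

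**5. Does the primary analysis depend on it?** SAP Section 5.3.2 fits the log titer on group alone and compares the lower 95% limit of the ratio with 0.67. Prior vaccination does not enter the model. It could act only through PPI exclusions. Those follow a list fixed before database lock and unblinding, and they cover only samples taken after a major deviation expected to affect immunogenicity. Nothing in either document makes the Section 2.3.1 sentence the source of such a deviation.

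**The case for a change.** The strongest contrary case has three parts.

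First, Inclusion Criterion 2 asks participants to keep to the prohibitions specified anywhere in the protocol, so a literal reader could treat the Section 2.3.1 sentence as binding. That reading is arguable, and it is why the wording should be made uniform. The documents give no sign that sites read it that way, and any question about the criteria has to go to the sponsor before enrolment.

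Second, the authors of the deviation list need one rule. That is true, but the list is not among the documents reviewed, so a defect in it would be a guess.

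Third, given the admitted data gap, one could ask for a supportive run that leaves out participants with a prior viral-vectored vaccine. The same rationale reports that studies of the sponsor's own Ad26 SARS-CoV-2 vaccine "have not shown a clear impact of baseline pre-existing Ad26 neutralizing antibodies on vaccine-induced responses". Prior COVID-19 vaccination is already tabulated by group in SAP Table 6. The share exposed is not given. Assuming 10%, 20% or 30%, the 105 per group would fall to about 94, 84 or 74, with power of about 87%, 83% or 78%. These figures price only that optional run. They do not measure the wording conflict, and the run would not resolve it.

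It is also tempting to blame an incomplete amendment, because the change table lists only Section 5.2 in the row stating that "Exclusion Criterion 10 was amended to allow the use of viral-vectored SARS-CoV-2 vaccines if administered at least 6 months prior to randomization". Section 6.8 is missing from that row too, yet it carries the 6-month wording, so the cause is not established.

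What stands is the contradiction itself.

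**Conclusion.** The inconsistency is certain, but it is clerical in weight: one sentence in a risk narrative differs from two operative sections that agree. No effect on enrolment, PPI membership, the 105 per group, the 90% power or the estimated ratio is shown. No change to the design or the statistical analysis follows.

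Section 2.3.1, Criterion 10.1c and Section 6.8 must still be reconciled. The choice of rule is the sponsor's. Protocol Section 10.3.1 limits clarification communications to text that does not alter study conduct, so a change to the eligibility criteria would need a formal amendment.

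This conclusion assumes that sites enrol by Section 5, as Section 2.3.3 states, and that the deviation list does not take its rule from the risk section. If that list did adopt the unlimited look-back, PPI membership would be affected and the point would need a fresh look.
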